THE IMPACT OF KETAMINE ON POSTOPERATIVE
COGNITIVE DYSFUNCTION, DELIRIUM, AND RENAL
DYSFUNCTION IN PATIENTS 70 YEARS OF AGE OR
OLDER AND UNDERGOING CARDIAC SURGERY.

NCT02554253

8/9/2017

THE IMPACT OF KETAMINE ON POSTOPERATIVE COGNITIVE
DYSFUNCTION, DELIRIUM, AND RENAL DYSFUNCTION IN PATIENTS 70
YEARS OF AGE OR OLDER AND UNDERGOING CARDIAC SURGERY.

IRB Approved 8/9/2017

Principle Investigator:

[name].
Assistant Professor of Anesthesiology
Mayo Clinic College of Medicine
Email: [contact]

Co-Principle Investigator:

[name].
Assistant Professor of Anesthesiology
Mayo Clinic College of Medicine
Email: [contact]

Co-Investigator:

[name]., L.P.
Assistant Professor of Psychology
Mayo Clinic College of Medicine
Email: [contact]

Statistician:

[name]
Assistant Professor of Biostatistics
Mayo Clinic College of Medicine
Email: [contact]

Coordinator

[name]
Study Coordinator
Anesthesia Clinical Research Unit
Mayo Clinic
Email: [contact]

RESEARCH PLAN

We propose a prospective study in which the effects of ketamine in cardiac surgery are investigated in adult patients undergoing cardiac surgical procedures requiring cardiopulmonary bypass (CPB). Ketamine has been demonstrated to have an anti-inflammatory effect as shown by reductions in Interleukin 6 (IL-6) levels. Postoperative dysfunctions in which inflammation has been implicated may be reduced by this anti-inflammatory effect. Use of inotropic and vasopressor support, hemodynamic variables, incidence of renal and cognitive dysfunction, and incidence of delirium will be assessed. Specifically, we will test the hypothesis that ketamine provides anti-inflammatory effects in this population of patients undergoing surgery requiring CPB and that the incidence of renal and cognitive dysfunction and delirium will be decreased.

Background and Significance

Ketamine is an FDA approved nonbarbiturate anesthetic and acts as a N-methyl-D-aspartate (NMDA) receptor antagonist. This medication is commonly used in the induction of anesthesia as well as in the performance of sedation for procedures. Ketamine has been demonstrated in several studies to have anti-inflammatory effects.[1-4] In cardiac surgical patients, the inflammatory response stimulated by undergoing CPB is thought to contribute to postoperative organ system dysfunction and morbidity. A reduction in inflammatory mediators has been shown in patients receiving ketamine prior to undergoing cardiac surgical procedures, including reductions in IL-6, cardiac troponin I (cTnI) and creatine kinase MB (CK-MB). IL-10 has anti-inflammatory effects and has been shown to be increased in patients who received preoperative ketamine compared

with patients who did not receive ketamine.[1, 4] In a group of patients who did not receive ketamine, IL-6 values peaked at 6 hours following aortic cross clamp removal, but this rise and peak was not seen in the group of patients who received a continuous ketamine infusion.[4]

A review and meta-analysis examined 14 studies involving 684 patients undergoing a variety of surgical procedures including coronary artery bypass graft (CABG) surgery. This concluded that ketamine does decrease IL-6 concentration. Elevations in IL-6 have been associated with ventricular wall motion abnormalities, perioperative complications, postoperative hyperdynamic instability, postoperative cognitive dysfunction, renal dysfunction, severity of acute respiratory distress syndrome (ARDS), and morbidity and mortality in children after cardiac surgery.[1, 5]

Results are conflicting regarding the impact of ketamine on CRP. In two reports postoperative CRP levels were lower in the group of patients who received pre-operative ketamine compared to those who received placebo.[2, 6] However, in a study comparing patients receiving a continuous ketamine infusion versus those not receiving ketamine, IL-6 and IL-8 levels were reduced in the ketamine group, but CRP levels were not different at 24 hours postoperatively.[4]

Postoperative cognitive dysfunction and postoperative delirium are important areas of morbidity following cardiac surgery. Unrelated to cardiac surgery, a systematic review confirmed an association between elevated inflammatory markers and poor cognitive outcomes.[7] In cardiac surgical patients, elevated IL-6 and CRP levels have been shown to be associated with worse cognitive function following CABG surgery.[6] Ketamine is thought to be neuroprotective, with multiple possible mechanisms having

been proposed, although the exact mechanism has not yet been elucidated.[2] Interestingly, ketamine has been shown to be associated with a decreased incidence of delirium and these patients also had lower postoperative CRP levels. In this study the incidence of delirium was reduced from 31% in the control group to 3% in the ketamine group.[2] In patients undergoing cardiac surgery polymorphisms in the 5HT2a receptor gene and NMDA receptor 3A and 2B subunits genes were investigated for association with postoperative delirium. A genetic variation, the presence of the AG haplotype of the GRIN3A gene, of the NMDA receptor was independently associated with postoperative delirium.[8] Additionally, when examining patients who developed delirium those with the AG haplotype suffered from delirium longer than patients with the GG haplotype. This may be a potential avenue by which ketamine impacts delirium. Postoperative delirium is associated with increased morbidity and mortality as well as increased hospital length of stay.[9, 10] If ketamine administration does prove to reduce delirium, it could make a significant impact on morbidity and mortality following cardiac surgery as delirium has proven difficult to prevent and treat.

Renal dysfunction is another significant area of morbidity in patients following cardiac surgery and has been associated with increased mortality.[11] Although no data has demonstrated an association between ketamine and a decrease in renal dysfunction, elevated postoperative IL-6 levels, measured 12 hours following surgery, have been associated with an increased incidence of renal dysfunction following surgery utilizing CPB.[5] One study demonstrated a decreased incidence of acute kidney injury (AKI) in patients who received propofol compared to those who received sevoflurane and another study demonstrated a decreased incidence of AKI in patients receiving a post-CPB

dexmedetomidine infusion.[12, 13] It is reasonable to postulate that the anti-inflammatory properties of ketamine as revealed by decreased levels of the inflammatory marker IL-6 may be associated with a decrease in postoperative renal dysfunction.

Patient age (> 65 years) and increased surgical complexity (with longer operative times) are known risk factors for postoperative cognitive dysfunction, delirium, and renal dysfunction.[14-16] These higher risk patients would be the population that would benefit most from the potential decrease in these important areas of morbidity.

Specific Aims/Hypotheses:

We aim to determine the impact of ketamine administration at induction of anesthesia on delirium, postoperative cognitive dysfunction, renal dysfunction, intra and postoperative hemodynamics, requirement for inotropic and vasopressor support, and postoperative mortality.

Specific Aim 1: 1. Determine the incidence of cognitive dysfunction and delirium in patients who receive ketamine for induction compared with those who receive propofol.

Specific Aim 2: Determine the impact of ketamine on patient hemodynamics as well as the dose of vasopressor and inotropes used during the intra and postoperative periods.

Specific Aim 3: Determine the incidence of renal dysfunction, defined by AKIN criteria, in patients who receive ketamine for induction compared with those who receive propofol.

STUDY DESIGN

We propose a prospective study in which patients will be randomized for induction with ketamine versus propofol (another regularly used anesthesia induction agent). Hemodynamics before, during and after cardiopulmonary bypass and use of inotropic and vasopressor medications will be recorded as per usual charting. The incidence of delirium, cognitive dysfunction, and renal dysfunction will be compared between the ketamine and propofol groups.

Inclusion/Exclusion Criteria

We will include patients age greater than or equal to 70 years presenting for cardiac surgery at the Mayo Clinic in Rochester, Minnesota. Patients will be eligible for inclusion if they are schedule to undergo complex cardiac surgery. Complex cardiac surgery will be defined as surgery involving more than one heart valve, redo-sternotomy procedures, or combined valvular and CABG procedures. Exclusion criteria will include left or right ventricular assist device implantation or explantation, procedures not requiring cardiopulmonary bypass, active infection or sepsis, severe hepatic disease or ascites, pre-operative renal dysfunction including a baseline creatinine equal to or greater than 2.0 mg/dL or requiring dialysis, immunosuppressive medication use (including steroid use), immunodeficiency syndrome, known neurologic or psychiatric disorder, or use of drugs for psychosis.

Number of Subjects

The incidence of renal dysfunction in patients following cardiac surgery has been reported to be anywhere from 21% to 38%.[13, 17, 18] The incidence of delirium after cardiac surgery has been reported over a broad range including 18% to 31%.[2, 14] Assuming a reduction in the incidence of renal dysfunction and delirium of approximately 10%, an appropriate sample size would be approximately 20 patients per group. We will plan to recruit 26 patients in each group.

Randomization and Consent

Written, informed consent will be obtained. The study will be minimal risk and non-invasive. Ketamine and propofol are both standard and commonly used medications for the induction of anesthesia. All aspects of care will be as per usual for patients undergoing these operations at The Mayo Clinic. Subjects will be recruited by letter via review of the surgical listing and scheduled for a preoperative appointment to review the study and obtain consent. Randomization will occur via delivery of a sealed envelope by a member of the study staff who is not directly involved with patient care on the morning of surgery to the consultant anesthesiologist assigning the patient to the ketamine or propofol group.

Human Subjects

Detailed Description: The human subjects will be prospectively studied after being randomized to receive one of two commonly used anesthesia induction agents.

Population: The subject population in this study will include all patients admitted to Mayo Clinic Rochester for cardiac surgery that meet the inclusion criteria. No specific populations (regardless of race, ethnicity or gender) will be excluded from this study aside from those who meet the exclusion criteria described above.

Research Materials: Electronic data will be stored securely and only accessed by those authorized on the IRB application.

The study will be minimal risk and written, informed consent will be obtained.

Potential Risks: This study compares two commonly used anesthetic agents. This study will not increase the risk of physical harm beyond what the surgical procedure naturally carries. The only potential risk is a breach of confidentiality, but this is thoroughly addressed as described below.

Protection: Data will be collected and stored on a secure Mayo server in a password-locked folder. No patient names will be stored, and the only identifiers included in the data will be clinic number, date of birth and date of admission. Only investigators authorized by the IRB will be allowed access to the study data.

Protocol/Methods

After written, informed consent is obtained the following baseline cognitive function studies will be administered by the anesthesia clinical research unit: Trail-making test, the Mini-Mental State Examination, Hopkins Verbal Learning Test (Revised forms 1 and 2), Digit Span forward and backward, Controlled Oral Word Association, and Stroop Test.

Anesthetic management will be directed by the consultant anesthesiologist as per routine aside from the following: Patients will be randomized to ketamine (1-2 mg/kg) versus propofol (0.5-1 mg/kg) induction with additional medication administered as needed to achieve intubating conditions. Inhalation anesthetic for induction in

combination with either propofol or ketamine will be permitted. The ketamine group will not receive propofol and vice versus. Maximum fentanyl bolus dosing will be 10 µg/kg, consistent with the currently implemented cardiac surgery rapid recovery protocol. Albumin administration will be avoided, but ultimately left to the discretion of the consultant anesthesiologist. Invasive monitoring techniques will be left to the discretion of the consultant anesthesiologist as per routine.

All other aspects of patient care will be as per routine including administration of inotropic or vasopressors as needed at the discretion of the anesthesiologist and /or cardiac surgical team. Administration of inotropic or vasopressors will be recorded in the anesthesia record as per usual practice. Propofol or dexmedetomidine infusions will be utilized for sedation at the end of the procedure as per usual practice.

The Confusion Assessment method for the ICU (CAM ICU) score will be recorded every 12 hours in the ICU as per routine. After dismissal from the ICU, a CAM score will be reviewed until hospital discharge. Prior to hospital discharge or within 1- 2 days prior to discharge, the patient will undergo post-intervention cognitive function studies administered by the anesthesia clinical research unit: Trail-making test, the Mini-Mental State Examination, Hopkins Verbal Learning Test (Revised forms 1 and 2), Digit Span forward and backward, Controlled Oral Word Association, and Stroop Test.

Outcome measurements

After inclusion in the study, demographic and medical data from all patients including age, height, weight, medical co-morbidities and current medications will be recorded and saved in the database. In addition, information regarding the planned procedure and the specifics of each patient's cardiac disease including ventricular

function, current cardiac anatomy and details of previous cardiac repairs will be recorded. Liver and renal function will be assessed by recording liver function tests and renal indices if available in the preoperative medication record.

Our primary outcomes will be the incidence of cognitive dysfunction and delirium as well as the incidence of renal dysfunction. Secondary outcomes will include assessing differences in hemodynamics, inotropic use and vasopressor use between the ketamine and propofol group. Mortality during admission for cardiac surgery will be assessed, however, the study will not be powered for this to be a primary outcome measure.

Data Analysis

Incidence of renal and cognitive dysfunction and delirium will be expressed as a percentage. Values will be compared between ketamine and non-ketamine groups using *t*-tests and ANOVA. A *P* value of less than 0.05 will be considered significant. Secondary outcomes will be analyzed using a *t*-test or ANOVA. All comparisons will be completed adjusting for multiple comparisons using the Bonferroni method.

References

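### About 20 patients per group is called appropriate for a 10% reduction, but a 10-point drop from the cited incidences needs 177–346 per group, and the planned 26 gives 13–20% power

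*Combined protocol and SAP*

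**What the plan says.** The whole sample-size rationale is one short paragraph under Number of Subjects. It gives the background rates for two outcomes: "The incidence of renal dysfunction in patients following cardiac surgery has been reported to be anywhere from 21% to 38" per cent, and "The incidence of delirium after cardiac surgery has been reported over a broad range including 18% to 31" per cent. It then assumes "a reduction in the incidence of renal dysfunction and delirium of approximately 10%, an appropriate sample size would be approximately 20 patients per group", and closes with "We will plan to recruit 26 patients in each group". It gives no power, sidedness, formula, chosen control rate or dropout rate, does not say whether the 10% is absolute or relative, and does not explain the step from 20 to 26.

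Under Outcome measurements, cognitive dysfunction, delirium and renal dysfunction are the primary outcomes, each as an incidence. Mortality is the only outcome that the plan says it is not powered for. Data Analysis specifies t-tests and ANOVA, says that a P "value of less than 0.05 will be considered significant", and adds: "All comparisons will be completed adjusting for multiple comparisons using the Bonferroni method".

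Background and Significance cites one earlier ketamine study in which "the incidence of delirium was reduced from 31% in the control group to 3% in the ketamine group". For renal dysfunction, the same section says that no data yet link ketamine to a reduction.

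**The concern.** Separating two proportions in the 20–40% range that differ by 10 points ordinarily takes hundreds of patients per group. A figure of 20 is about an order of magnitude too low, and no choice of the unstated inputs is offered that would explain it.

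The paragraph is the only justification for the trial's size, and it covers two of the three primary outcomes. If ketamine truly lowered an incidence by 10 points, 26 per group would miss it in about 80–87% of trials at unadjusted 0.05, and more often after Bonferroni. A reader told that the size was appropriate could then take a null result as evidence that ketamine does not help, when the trial had little chance of showing the effect it assumed.

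**Working it through.** **Inputs from the document**
- Control incidences p₁: 18% and 31% (delirium), 21% and 38% (renal dysfunction), from Number of Subjects.
- Reduction: about 10%, same section.
- Significance level: 0.05, with Bonferroni, from Data Analysis.
- Group size: 20 stated, 26 planned.

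**Assumptions, because the plan is silent:** 80% power; two-sided testing, with one-sided also shown; a 10-point absolute drop, with other readings also shown.

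**Step 1. Try to reproduce 20.** The standard two-proportion formula, with p̄ = (p₁ + p₂)/2, is

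n = [z₁₋α/₂ √(2p̄(1−p̄)) + z₀.₈ √(p₁(1−p₁) + p₂(1−p₂))]² / (p₁−p₂)²

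For 31% versus 21%, p̄ = 0.26:

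n = [1.960 × √0.3848 + 0.8416 × √0.3798]² / 0.01 = (1.2158 + 0.5187)² / 0.01 = 300.8, so 301 per group.

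| Drop | Two-sided n per group | One-sided n per group |
|---|---|---|
| 18% to 8% | 177 | 139 |
| 21% to 11% | 210 | 166 |
| 31% to 21% | 301 | 237 |
| 38% to 28% | 346 | 273 |

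The two-sided figures are 177/20 = 8.9 to 346/20 = 17.3 times the stated 20, and 177/26 = 6.8 to 346/26 = 13.3 times the planned 26.

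**Step 2. Try other readings and methods.**
- A fall *to* 10%: 36–295 per group two-sided, 28–232 one-sided.
- A 10% *relative* reduction: about 2,500–6,900 two-sided, about 2,000–5,400 one-sided.
- Unpooled, arcsine or continuity-corrected versions of the two-sided 10-point case: 172–366.
- 90% power, two-sided 10-point case: 236–463.

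For a 10-point drop, the only setting tried that came near 20 was a one-sided level of 0.20 with 50% power (17–32 per group). That contradicts the plan's 0.05. The figure of 20 is not reproduced.

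**Step 3. Power of the groups as planned.** Summing the binomial probabilities over all 2×2 tables that reject (uncorrected chi-square; the t-test gives the same values at 0.05):

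| Drop | n=20, two-sided | n=26, two-sided | n=26, one-sided | n=26, two-sided 0.05/3 |
|---|---|---|---|---|
| 18% to 8% | 14.6% | 19.6% | 29.9% | 6.2% |
| 21% to 11% | 13.4% | 17.5% | 26.4% | 5.9% |
| 31% to 21% | 11.3% | 13.8% | 20.6% | 5.6% |
| 38% to 28% | 10.7% | 12.8% | 20.0% | 5.3% |

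The last column assumes three primary comparisons; the plan gives no count. With six, power is about 3%. Fisher's exact test at unadjusted 0.05 gives 7–9% at n=26.

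**Step 4. What 26 per group can detect.** At two-sided 0.05 without adjustment, exact 80% power needs a fall from 38% to about 7.6%, from 31% to about 4%, or from 21% to about 0.3%. From 18%, even a fall to zero gives only 71%. For the cited 31% to 3%, power is 73% at n=20, 80% at n=23 and 86% at n=26.

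**Step 5. Precision.** The 95% half-width for a risk difference is 1.96 √[(p₁(1−p₁) + p₂(1−p₂))/26]. For 31% versus 21% it is 1.96 × √(0.3798/26) = 23.7 points. Across the four pairs it is 18.1, 19.7, 23.7 and 25.4 points, always wider than the 10-point effect.

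**The case against.** The strongest reply is that 177–346 and 13–20% rest on inputs the plan never states, so part of the fault is omission rather than wrong arithmetic. That is true of the exact figures. It does not rescue the conclusion, because every reasonable choice of power, sidedness and scale leaves 20 far short for the range of incidences cited.

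The closest alternative reading is a fall *to* 10% from the highest renal incidence, 38%. One-sided exact power is then 79.7% at n=26 and 69.8% at n=20. But the plan describes a reduction of that size, not a reduction to that level, and the other three incidences do not fit.

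The planned t-tests and continuous cognitive scores might suggest that the number came from a calculation on means. The document gives no such effect size and ties 20 explicitly to incidences.

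The 31%-to-3% result offers the best support for 26 per group, with 86% power. That holds only for the uncorrected test at unadjusted 0.05. Fisher's exact test gives 72%, and a Bonferroni level of 0.05/3 gives 65%. It is also a delirium result and a 28-point drop, so it supports neither the stated 10% nor the renal outcome.

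The study might also be excused as a pilot. The document never calls it one: the Research Plan says it will test a hypothesis that these incidences fall, and only mortality is described as unpowered.

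One caution stands. A trial of this size would sometimes detect a 10-point drop, so it would usually fail to separate that benefit from none, not always.

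**Conclusion.** The statement is wrong as written. Under two-sided 0.05, 80% power and a 10-point drop, all of which except the 0.05 are assumptions, the required size is 177–346 per group against a stated 20 and a planned 26. No reading of the 10% examined at 0.05 and 80% power, one- or two-sided, gives 20. The chance of detecting the assumed effect with 26 per group is 13–20% before Bonferroni, and these power figures are generous to the plan because it requires that adjustment. The planned 26 is defensible only for effects near 28–30 points from the higher cited incidences, at an unadjusted level. This must be corrected, because it is the only sizing argument for the primary outcomes. Cognitive dysfunction, also primary, has no sizing assumption at all.

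**What to change.** Keep 26 per group. In Number of Subjects, delete the claim that about 20 per group is appropriate for a 10% reduction and say what 26 delivers, for example:

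> At two-sided 0.05 without adjustment, 26 per group gives about 14% power for 31% versus 21% and about 13% for 38% versus 28%. Power reaches 80% only for a fall from 31% to about 4%, or from 38% to about 7.6%. Power is lower after the Bonferroni adjustment.

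State how many comparisons the Bonferroni adjustment covers, so that the adjusted power can be given too. If it is three, power for 31% versus 4% is about 58%. Say also that cognitive dysfunction was not used in sizing the trial.

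In Data Analysis, add the risk difference with its 95% confidence interval for each incidence outcome, noting an expected half-width of about 24 points for 31% versus 21%.

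The cost is a reworded paragraph and one added estimate per outcome. No extra patients are needed. The rewording does not raise the power; it makes the plan's claim match what the trial can show, and the stated figure becomes less favourable.

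### No sequence generation, blocks or strata are specified and no covariate is planned, although the plan names surgical complexity as a risk factor for every primary outcome

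*Combined protocol and SAP*

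**What the plan says.** - **Allocation (Randomization and Consent).** "Randomization will occur via delivery of a sealed envelope by a member of the study staff" who takes no direct part in the patient's care, on the morning of surgery. That is the whole rule. The text neither states nor excludes blocks, strata or a particular method of generating the sequence.
- **Size (Number of Subjects).** "We will plan to recruit 26 patients in each group", so 52 in total.
- **Risk factor (end of Background and Significance).** Together with age above 65, "increased surgical complexity (with longer operative times) are known risk factors for postoperative cognitive dysfunction, delirium, and renal dysfunction". The Outcome measurements section makes those same three conditions the primary outcomes.
- **Case mix (Inclusion/Exclusion Criteria).** Eligible complex surgery is defined as "surgery involving more than one heart valve, redo-sternotomy procedures, or combined valvular and CABG procedures".
- **Analysis (Data Analysis).** Incidences are compared by t-tests and ANOVA with a Bonferroni correction. No covariate is named.
- **Data already collected (Outcome measurements).** The planned procedure and details of earlier cardiac repairs are recorded for every patient.

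**The concern.** The plan itself identifies a prognostic factor common to all its primary outcomes. It then admits three kinds of operation that may differ on that factor, and it describes no step in design or analysis that takes account of it. With 52 patients, a moderate chance imbalance on surgery type is an ordinary event. If one occurs, a reader cannot easily separate the effect of the induction agent from a difference in case mix, and the planned comparison offers no pre-specified adjusted result. An adjustment chosen after the imbalance is seen would be less convincing than one fixed beforehand.

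**Working it through.** **Inputs.** From the plan: 26 per group, and reported incidences of 21% to 38% (renal dysfunction) and 18% to 31% (delirium). Assumed, because the plan gives no expected surgery mix or risk by type: a binary surgery-type stratum holding 30-50% of patients, and a 20-point difference in risk between its two levels.

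**The plan's own figure.** The calculated 20 per group does not follow from a 10-point absolute reduction. With a two-sided 5% level and 80% power (assumed), the two-proportion formula gives 177 per group for 18% versus 8% and 346 for 38% versus 28%. That is a separate problem. Only the 26 per group is used below.

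**Step 1: chance of imbalance with totals fixed at 26/26 and no strata.** If K of the 52 patients are in the stratum, the number *a* in one arm is hypergeometric (52, K, 26), and the gap between arms is |2a − K| patients. The chance of a gap of 5 or more is:

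| K (share of 52) | P(gap ≥ 5) |
|---|---|
| 16 (31%) | 0.13 |
| 17 (33%) | 0.24 |
| 21 (40%) | 0.26 |
| 25 (48%) | 0.27 |
| 26 (50%) | 0.16 |

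The values alternate because the gap has the same parity as K: for even K the smallest qualifying gap is 6. If K is left random, with A and B each Bin(26, p), then P(|A − B| ≥ 5) = 0.172, 0.202 and 0.212 for p = 0.3, 0.4 and 0.5. A gap of 5 patients is 5/26 = 19 points.

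**Step 2: all three surgery types.** Four assumed mixes were simulated (17/17/18, 26/13/13, 32/10/10 and 10/14/28), treating the types as exclusive. The chance that at least one type differs by 20 points or more is 21-26% with totals fixed at 26/26. Equal arm sizes therefore do not remove the problem. With blocks of 4 within type, the largest simulated gap was 8 to 10 points.

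**Step 3: what such a gap would do.** Conditional on a 19-point gap and the assumed 20-point risk contrast, the observed difference in incidence moves by 0.19 × 20 = about 4 points. The standard error of that difference is √(2q(1−q)/26). This gives 10.7 points at q = 0.18 and 13.5 points at q = 0.38.

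**Step 4: what adjustment would gain.** A stratum of share w with risk contrast 0.20 explains w(1−w) × 0.20² / [q(1−q)] of the outcome variance. At w = 0.5 and q = 0.30 this is 0.25 × 0.04 / 0.21 = 4.8%, and the standard error falls from 12.7 to 12.7 × √0.952 = 12.4 points. Over w = 0.3-0.5 and q = 0.18-0.38, the share explained is 3.6% to 6.8% and the fall is about 0.2 to 0.4 points. That is worth about 2 to 4 extra patients (52/0.964 = 54; 52/0.932 = 56).

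**The case against.** Several stronger readings are tempting, and the documents do not support them.

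- **That allocation is unrestricted.** A reader might infer this from the bare envelope sentence. The plan is silent, and 26 in each group is what a restricted sequence would deliver. Only the lack of specification can be asserted.
- **That unequal arms are a hazard.** This presupposes simple randomisation, which is nowhere stated. Even a 22/30 split keeps 4 × 22 × 30 / 52² = 97.6% of the efficiency of 26/26.
- **That imbalance biases the result.** Chance imbalance is already part of the randomisation variance, so the test remains valid. The 4-point figure is a shift conditional on an unlucky allocation. It rests on a risk contrast the plan does not give, and it is about a third of one standard error.
- **That redo surgery is the high-risk stratum.** All three categories are defined as complex and nothing ranks them. Restricting entry to complex surgery and to age 70 or over already narrows both named risk factors. The categories can also overlap, as in a redo multi-valve operation.

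These objections limit the size of the point and how it may be worded. They do not remove it: the plan ties risk to complexity and operative time, nothing shows that the entry criteria abolish that gradient, and no provision is made for it although the relevant data are recorded.

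**Conclusion.** The point holds as a modest, inexpensive improvement to the stated design and analysis. The allocation scheme is not specified, and the plan's own named risk factor appears in no stratification or adjustment. A gap of 5 or more patients on a surgery-type stratum has a probability of about 13% to 27% with totals fixed at 26/26, given an assumed stratum share of 30-50%. The consequence is some lost precision and a less interpretable comparison. The benefit of adjustment is small, about 0.2 to 0.4 points on a standard error of roughly 11 to 13.5 points, and that figure depends on the assumed 20-point contrast. Surgery type is also only a proxy for complexity.

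**What to change.** 1. **Data Analysis.** Before any outcome is seen by group, add text such as: 'Each primary outcome will be compared between groups with redo sternotomy (yes/no) included as a factor, and the adjusted difference in incidence will be reported.' Redo status is an example. The investigators should confirm which recorded split best reflects complexity. A single binary factor avoids the overlap between the three categories, and the extra term adds no treatment comparison to the Bonferroni count.
2. **Randomization and Consent.** State how the sequence is generated and whether it is blocked or stratified. If envelopes are not yet prepared, use sequentially numbered opaque envelopes in randomly permuted blocks of mixed size within the chosen factor. If they are already prepared, describe the scheme used and rely on item 1. Blocking without strata would not balance surgery type.

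**Cost.** One model term and a second envelope stack. A partly filled last block may leave the arms one or two patients apart in each stratum. With blocks of at most 4 in two strata the worst total is 2 + 2 = 4, a 24/28 split, which keeps 4 × 24 × 28 / 52² = 99.4% of the efficiency.

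### Does the bar on propofol in the ketamine group conflict with propofol sedation at the end of surgery?

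*Combined protocol and SAP*

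**What the plan says.** The randomised contrast is the induction agent. Study Design says that "patients will be randomized for induction with ketamine versus propofol", and Human Subjects describes patients as "randomized to receive one of two commonly used anesthesia induction agents". The opening sentence of Specific Aims/Hypotheses reads "We aim to determine the impact of ketamine administration at induction of anesthesia on delirium, postoperative cognitive dysfunction, renal dysfunction" before it goes on to further outcomes.

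The exceptions to routine anesthetic care are in Protocol/Methods, in a paragraph that opens "Anesthetic management will be directed by the consultant anesthesiologist as per routine aside from the following". It gives the two induction regimens, then allows an inhaled agent alongside either drug during induction, and then states that "The ketamine group will not receive propofol and vice versus". Rules on fentanyl, albumin and monitoring follow.

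The next paragraph of that section begins "All other aspects of patient care will be as per routine" and ends with the sedation sentence: "Propofol or dexmedetomidine infusions will be utilized for sedation at the end of the procedure as per usual practice". It names no arm.

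**The concern.** Taken alone, the exclusivity sentence has no limit in time. A ketamine patient sedated with a propofol infusion after surgery would then breach one sentence of Protocol/Methods while following another.

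If staff applied the sentence throughout the hospital stay, ketamine patients could receive only dexmedetomidine at the end of the procedure, while propofol patients could receive either drug. The arms would then differ in sedation as well as induction, and a difference in a primary outcome could not be attributed cleanly to the induction agent.

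The subject is not remote from the outcomes. The Background cites one study with less acute kidney injury under propofol than under sevoflurane, and another with less after a post-bypass dexmedetomidine infusion. Renal dysfunction is a primary outcome.

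**Working it through.** The plan states no figure on this point, so there is nothing to reproduce. The check compares two readings of the exclusivity sentence with the rest of the text.

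**Inputs.** 26 patients per group (Number of Subjects), so 2 × 26 = 52 in total. Two named end-of-procedure sedatives, propofol and dexmedetomidine (Protocol/Methods).

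**Step 1: what each reading allows.**

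| Reading of the rule | Named sedatives open to ketamine arm | Named sedatives open to propofol arm |
|---|---|---|
| All phases of care | 1 of 2 | 2 of 2 |
| Induction only | 2 of 2 | 2 of 2 |

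The converse half of the rule, no ketamine in the propofol group, causes no conflict, because ketamine is not a named sedative.

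**Step 2: which reading fits the text.**

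- *Neighbouring sentences.* The two sentences just before the rule concern induction: the randomised regimens, then permission to add an inhaled agent to either drug. The rule completes the sequence. An inhaled agent may be combined with either drug, but the two drugs may not be combined with each other.
- *Aims and randomisation.* Both are set at induction, and Aims 1 and 3 again define the ketamine group by its use for induction.
- *Sedation sentence.* It falls under the paragraph on all other care, which separates it from the exceptions listed before it. It names propofol as a drug in usual use. Randomisation and Consent likewise says that care will be as usual for these operations. A bar on propofol sedation in the ketamine arm would fit these statements only if usual practice gave those patients dexmedetomidine anyway.

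Induction-only is therefore compatible with every statement, whereas the all-phases reading strains at least two.

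**Step 3: size under the all-phases reading.** Let *u* be the share of propofol-arm patients given a propofol infusion. The ketamine-arm share would be 0 by rule, so the difference between arms is *u* − 0 = *u*. The documents do not give *u*. Its limits are 0/26 = 0 and 26/26 = 100 percentage points, which hold for any proportion and carry no information. Under the induction-only reading the rule imposes no difference.

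**Step 4: does any planned analysis depend on the scope?** Groups are formed by the sealed envelope (Randomization and Consent) and compared as ketamine against propofol, or non-ketamine (Study Design; Data Analysis). A ketamine patient later given a propofol infusion did receive ketamine and was assigned to it, so the patient counts in the ketamine group under either reading. The plan defines no per-protocol set and no exclusion for deviations. Whether the infusion is called a deviation changes no numerator or denominator.

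**The case for a change.** The best case for acting is that induction-only is an inference. The paragraph that holds the rule also covers matters outside induction, for example "Albumin administration will be avoided, but ultimately left to the discretion of the consultant anesthesiologist", so position alone does not fix the scope. The consultant anesthesiologist who receives the envelope knows the arm and directs the anesthetic. Someone who reads the rule broadly might withhold propofol sedation from ketamine patients only, and sedation could then drift apart between arms before the ICU delirium assessments.

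Part of this stands. The scope is not written down, and the same infusion would be compliant on one reading and a deviation on the other.

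The rest does not carry. The albumin and monitoring sentences come after the rule, whereas the sentences leading into it concern induction. The monitoring sentence is also a weak example of an exception, since it leaves monitoring to routine. If sedation did drift by arm, it would do so after randomisation and as a result of it. The groups would still be comparable at baseline, and what would change is the interpretation of the contrast. That consequence needs the reading the text favours least.

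The link to outcomes is thin as well. The propofol finding is against sevoflurane and is not described as end-of-procedure sedation, and the documents tie neither sedative to delirium or cognitive dysfunction. Sedative agent and dose are not named among the study data, but that list is introduced as a partial one, so it does not show that they will go unrecorded.

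**Conclusion.** This is a gap in wording that readers of the protocol can fill sensibly from context. On the natural reading, the rule keeps the two induction agents apart and does not reach end-of-procedure sedation. The randomised comparison of 26 against 26 patients is then unaffected. No bias, confounding or miscounting is shown, and the documents allow no effect on any outcome to be calculated.

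The conclusion rests on two assumptions: that the sentences around the rule set its scope, and that patients are analysed in the group to which the envelope assigned them, which is the plain sense of the text.

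The two sentences in Protocol/Methods must be reconciled by stating which phase of care the rule covers. That choice belongs to the clinical team, and this review does not make it. A table of end-of-procedure sedative by arm, taken from the existing record, would be a reasonable descriptive addition, but it would correct no result. Neither step alters an outcome, a comparison or the sample size.
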